5.5.1 Time Period and Frequency for Collecting AE and SAE Information

All solicited AEs that occur within 7 days and unsolicited AEs for 21 days following the administration of *Fluarix Tetra* must be recorded into the appropriate section of the eCRF, irrespective of intensity, as reported by the participant in the completed diary card.

All SAEs regardless of possible relation to vaccination should be reported in an expedited way throughout the study.

The Investigator or designee will record and immediately report to the Sponsor or designee all SAEs in enrolled participants occurring within 21 days post-vaccination via the eCRF. Reporting should, under no circumstances, occur later than 24 hours after the Investigator becomes aware of

CONFIDENTIAL

Phase IV Clinical Trial Protocol

GlaxoSmithKline
A phase IV trial of *Fluarix Tetra* in Indian
adults aged 65 years and older
Version 2.0, dated: 05 May 2023
Protocol/ Study No.: 218702
Page 41 of 74

the SAE. The Investigator will submit any updated SAE data to the Sponsor within 24 hours of it being available.

Medical occurrences that begin before the start of receipt of trial vaccine but after obtaining informed consent will be recorded on the Medical History/ Current Medical Conditions section of the eCRF, not the AE section.

Investigators are not obligated to actively seek AE or SAE after conclusion of the trial participation. However, if the Investigator learns of any SAE, including a death, at any time after a participant has been discharged from the trial, and he/she considers the event to be reasonably related to the trial treatment or trial participation, the Investigator must promptly notify the Sponsor.

5.5.2 Method of Detecting AEs and SAEs

A diary card will be used in this trial to capture solicited and other AEs. In addition to the participant completing and returning the diary card, the Investigator will record any occurrence of SAEs into the participant's eCRF to minimize potential missing data (e.g., when a participant's hospitalization prevents the completion of the diary). An AE that is assessed as severe should not be confused with a SAE. Severity is a categorization used for rating the intensity of an event; and both AEs and SAEs can be assessed as severe. An event is defined as 'serious' when it meets 1 of the pre-defined outcomes as described above ([Section 5.5](#)).

Assessment of Intensity

The intensity of the following solicited AEs will be assessed as described:

Table 3. Intensity Scales for Solicited Events in Adults 18 years of Age or More

Event	Intensity Grade	Parameter
Pain at administration-site	0	None
	1	Mild: Any pain neither interfering with nor preventing normal everyday activities
	2	Moderate: Painful when limb is moved and interferes with everyday activities
	3	Severe: Significant pain at rest. Prevents normal everyday activities
Headache	0	Normal
	1	Mild: Headache that is easily tolerated

CONFIDENTIAL
Phase IV Clinical Trial Protocol

GlaxoSmithKline
 A phase IV trial of *Fluarix Tetra* in Indian
 adults aged 65 years and older
 Version 2.0, dated: 05 May 2023
 Protocol/ Study No.: 218702
 Page 42 of 74

Event	Intensity Grade	Parameter
	2	Moderate: Headache that interferes with normal activity
	3	Severe: Headache that prevents normal activity
Fatigue	0	Normal
	1	Mild: Fatigue that is easily tolerated
	2	Moderate: Fatigue that interferes with normal activity
	3	Severe: Fatigue that prevents normal activity
Muscle ache all over body	0	Normal
	1	Mild: Muscle aches that are easily tolerated
	2	Moderate: Muscle aches that interfere with normal activity
	3	Severe: Muscle aches that prevent normal activity
Joint pain	0	Normal
	1	Mild: Joint pain that is easily tolerated
	2	Moderate: Joint pain that interferes with normal activity
	3	Severe: Joint pain that prevents normal activity
Shivering (chills)	0	Normal
	1	Mild: Shivering (chills) that is easily tolerated
	2	Moderate: Shivering (chills) that interferes with normal activity
	3	Severe: Shivering (chills) that prevents normal activity
Sweating	0	Normal
	1	Mild: Sweating that is easily tolerated
	2	Moderate: Sweating that interferes with normal activity
	3	Severe: Sweating that prevents normal activity
Gastrointestinal symptoms: nausea, vomiting, diarrhea and/or abdominal pain	0	Normal
	1	Mild: Gastrointestinal symptoms that are easily tolerated
	2	Moderate: Gastrointestinal symptoms that interfere with normal activity
	3	Severe: Gastrointestinal symptoms that prevent normal activity
Redness at administration-site		Record greatest surface diameter in mm
Swelling at administration-site		Record greatest surface diameter in mm
Temperature*		Record temperature in °C/°F

* Fever is defined as temperature $\geq 38.0^{\circ}\text{C}$ (100.4°F) by any route. The preferred location for measuring temperature will be the oral route.

The maximum intensity of local injection site redness/swelling will be scored at GSK as follows:

0: ≤ 20 mm
 1: > 20 to 50 mm

CONFIDENTIAL

Phase IV Clinical Trial Protocol

GlaxoSmithKline
A phase IV trial of *Fluarix Tetra* in Indian
adults aged 65 years and older
Version 2.0, dated: 05 May 2023
Protocol/ Study No.: 218702
Page 43 of 74

2: >50 to 100 mm
3: >100 mm

The maximum intensity of fever will be scored at GSK as follows:

0:	<38.0°C (<100.4°F)
1:	≥38.0–38.4°C (≥100.4–101.2°F)
2:	≥38.5–38.9°C (≥101.3–102.1°F)
3:	≥39.0–40.0°C (≥102.2–104.0°F)
4:	>40.0°C (>104.0°F)

The Investigator will assess the maximum intensity that occurred over the duration of the event for all unsolicited AEs (including SAEs) recorded during the study. The assessment will be based on the Investigator's clinical judgment.

The intensity should be assigned to one of the following categories:

1 (mild)	= An AE which is easily tolerated by the participant, causing minimal discomfort, and not interfering with everyday activities.
2 (moderate)	= An AE which is sufficiently discomforting to interfere with normal everyday activities.
3 (severe)	= An AE which prevents normal, everyday activities In adults, such an AE would, for example, prevent attendance at work/school and would necessitate the administration of corrective therapy.

An AE that is assessed as Grade 3 (severe) should not be confused with an SAE. Grade 3 is a category used for rating the intensity of an event; and both AEs and SAEs can be assessed as Grade 3. An event is defined as 'serious' when it meets 1 of the pre-defined outcomes as described in the [Section 5.5](#).

CONFIDENTIAL

Phase IV Clinical Trial Protocol

GlaxoSmithKline
A phase IV trial of *Fluarix Tetra* in Indian
adults aged 65 years and older
Version 2.0, dated: 05 May 2023
Protocol/ Study No.: 218702
Page 44 of 74

Assessment of causality

All solicited administration-site and systemic events will be considered causally related to vaccination. The complete list of these events is provided in the [Table 5](#).

The Investigator must assess the relationship between study vaccine/product and the occurrence of each unsolicited AE/SAE using clinical judgment. Where several different vaccines/products were administered, the Investigator should specify, when possible, if the unsolicited AE/SAE could be causally related to a specific vaccine/product (i.e., investigational, control/placebo or co-administered vaccine). When causal relationship to a specific vaccine/product cannot be determined, the Investigator should indicate the unsolicited AE/SAE to be related to all products.

Alternative plausible causes, such as natural history of the underlying diseases, concomitant therapy, other risk factors, and the temporal relationship of the event to the study vaccine/product will be considered and investigated. The investigator will also consult the investigator brochure (IB) to determine his/her assessment.

Causality should be assessed by the Investigator using the following question:

Is there a reasonable possibility that the unsolicited AE may have been caused by the study vaccine/product?

YES	:	There is a reasonable possibility that the study vaccine/product contributed to the AE.
NO	:	There is no reasonable possibility that the AE is causally related to the administration of the study vaccine/product. There are other, more likely causes and administration of the study vaccine/product is not suspected to have contributed to the AE.

If an event meets the criteria to be determined as ‘serious’ (see [Section 5.5](#)), additional examinations/tests will be performed by the Investigator to determine ALL possible contributing factors for each SAE.

Possible contributing factors include:

- Medical history.
- Other medication.

CONFIDENTIAL

Phase IV Clinical Trial Protocol

GlaxoSmithKline
A phase IV trial of *Fluarix Tetra* in Indian
adults aged 65 years and older
Version 2.0, dated: 05 May 2023
Protocol/ Study No.: 218702
Page 45 of 74

- Protocol required procedure.
- Other procedure not required by the protocol.
- Lack of efficacy of the vaccine/product, if applicable.
- Erroneous administration.
- Other causes: There may be situations when an SAE has occurred, and the Investigator has minimal information to include in the initial report to GSK. However, it is very important to record an assessment of causality for every event.

The causality assessment is one of the criteria used when determining regulatory reporting requirements. The Investigator may change his/her opinion of causality after receiving additional information and update the SAE information accordingly.

(1) Medically attended visits

For each solicited and unsolicited symptom the participant experiences, the participant will be asked if he/she received medical attention defined as hospitalization, or an otherwise unscheduled visit to or from medical personnel for any reason, including emergency room visits. This information will be recorded in the eCRF.

(2) Assessment of outcomes

The Investigator will assess the outcome of all unsolicited AEs (including SAEs) recorded during the study as:

- Recovered/resolved.
- Recovering/resolving.
- Not recovered/not resolved.
- Recovered with sequelae/resolved with sequelae.
- Fatal (SAEs only).

CONFIDENTIAL

Phase IV Clinical Trial Protocol

GlaxoSmithKline
A phase IV trial of *Fluarix Tetra* in Indian
adults aged 65 years and older
Version 2.0, dated: 05 May 2023
Protocol/ Study No.: 218702
Page 46 of 74

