Protocol/ Study No.: 218702
Page 17 of 74

Safety:

All the AEs, SAEs and other safety reporting data will be collected as per GSK standard procedures:

- Recording of solicited AEs for 7 days after vaccination
- Recording of unsolicited AEs for 21 days after vaccination
- Recording of SAEs for 21 days after vaccination
- AEs leading to discontinuation

Trial participants will be provided with a diary card at the time of vaccination to record the occurrence and intensity of solicited local and general AEs during the first 7 days after vaccination and of unsolicited AEs within 21 days after vaccination. These diary cards will be reviewed at the trial visit following the vaccination visit. All solicited local AEs will be considered to be causally related to vaccination. Causality of all other AEs will be assessed by the Investigator. Any AEs and SAEs reported after 21 days will be reported by the Investigator as per Indian regulatory requirement.

Statistical Considerations:

Sample size: Approximately 250 participants will be enrolled in this trial to achieve 200 evaluable participants considering 20% (N=50) of participants for possible drop-outs or invalid data.

With N=250, the width of the 95% CIs for the incidences correspond to the very common ($\geq 1/10$) AEs will always be $< 13\%$, and for uncommon and common AEs it will be $\leq 3\%$. The probability of observing at least 1 participant with an AE will be above 91% for common and very common AEs.

Interim and Final Analyses: There will be no interim analysis. The final analysis will be performed when all data, up to the end of the trial, are available and completely cleaned.

CONFIDENTIAL

Phase IV Clinical Trial Protocol

GlaxoSmithKline
A phase IV trial of *Fluarix Tetra* in Indian
adults aged 65 years and older
Version 2.0, dated: 05 May 2023
Protocol/ Study No.: 218702
Page 18 of 74

Ethical and Regulatory Considerations:

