5.5 Adverse Events

Definition of AE: An AE is any untoward medical occurrence (an unfavorable/unintended sign - including an abnormal laboratory finding), symptom, or disease (new or exacerbated) in a trial participant that is temporally associated with the administration of a marketed vaccine. The AE may or may not be considered related to the marketed vaccine.

Events Meeting the AE Definition:

- Significant or unexpected worsening or exacerbation of the condition/indication under trial.
- Exacerbation of a chronic or intermittent pre-existing condition including either an increase in frequency and/or intensity of the condition.
- New conditions detected or diagnosed following the performance of the administration of marketed vaccine even though they may have been present before trial start.
- Signs, symptoms, or the clinical sequelae of a suspected drug, disease, or other interaction.
- Signs, symptoms, or the clinical sequelae of administration error of either the marketed vaccine or a concurrent medication.
- Signs or symptoms temporally associated with the marketed vaccine.
- Signs, symptoms that require medical attention (e.g., hospital stays, physician visits and emergency room visits).
- Significant failure of an expected pharmacologic or biological action.
- Clinically significant abnormal laboratory findings or other abnormal assessments that are present at baseline and significantly worsen following the start of the trial will also be reported as AEs or SAEs.
- The signs, symptoms, and/or clinical sequelae resulting from lack of efficacy will be reported as AE or SAE if they fulfill the definition of an AE or SAE.

Events NOT Meeting the AE Definition

- Situations where an untoward medical occurrence did not occur (e.g., social and/or convenience admission to a hospital, admission for routine examination).
- Anticipated day-to-day fluctuations of pre-existing disease(s) or condition(s) present or detected at the start of the trial that do not worsen.

CONFIDENTIAL

- Pre-existing conditions or signs and/or symptoms present in a participant before the administration of the trial vaccine. These events will be recorded in the medical history section of the eCRF.
- Hospitalization for elective treatment of a pre-existing condition (known or diagnosed before signing the informed consent) that did not worsen from baseline.

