4.2. Primary Endpoint(s) Analyses

4.2.1. Definition of Endpoints

Number and percentage of subjects with solicited AEs (administration-site as well as systemic) for 7 days from the reference start date (Day 1).

Number and percentage of subjects with unsolicited AEs starting from reference start date for 21 days i.e. up to Day 21.

Number and percentage of subjects with SAEs from the reference start date for 21 days i.e. up to Day 21.

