4.4.1.5. Assessment of Causality

Causality is not assessed for solicited AEs. For unsolicited AEs, the investigator must assess the relationship between study vaccine and the occurrence of each unsolicited AE/SAE using clinical judgement.

Causality should be assessed by the investigator using the following question: Is there a reasonable possibility that the unsolicited AE may have been caused by the study vaccine/product?

YES: There is a reasonable possibility that the study vaccine/product contributed to the AE.

NO: There is no reasonable possibility that the AE is causally related to the administration of the study vaccine/product. There is other, more likely cause and administration of the study vaccine/product is not suspected to have contributed to the AE.

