6.2. Appendix 2 Data Derivations Rule

6.2.1. Number of Occurrences of Each AE

For solicited administration-site and systemic AEs, the number of occurrences will be:

Equal to zero if the leading question ‘Did the AE occur?’ is ‘No’ or ‘Not done/Unknown’.

Equal to one if the leading question ‘Did the AE occur?’ is ‘Yes’.

For unsolicited AE, AEs with different PTs and/or start dates will be counted as distinct occurrences in a same patient.

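### The protocol's exclusion of pre-existing symptoms is not carried into the counting of solicited events, so unchanged background symptoms can enter the primary reactogenicity results

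*Protocol*

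**What the plan says.** Protocol 5.5 lists among events that do not meet the AE definition "Pre-existing conditions or signs and/or symptoms present in a participant before the administration of the trial vaccine". It sends them to the medical history section of the eCRF. The same list excludes expected day-to-day variation of existing conditions that does not worsen, while a real exacerbation does count as an AE.

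Solicited events follow a different route. The diary card is issued at vaccination (Protocol synopsis, Safety). Under Protocol 5.5.1 its content is entered "irrespective of intensity, as reported by the participant in the completed diary card". SAP 6.2.1 sets the number of occurrences "Equal to one if the leading question ‘Did the AE occur?’ is ‘Yes", with no condition on pre-dose status. The primary endpoint in SAP 4.2.1 is "Number and percentage of subjects with solicited AEs (administration-site as well as systemic) for 7 days from the reference start date (Day 1").

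On causality, Protocol 5.5.2 says "All solicited administration-site and systemic events will be considered causally related to vaccination". The synopsis says "All solicited local AEs will be considered to be causally related to vaccination", and then "Causality of all other AEs will be assessed by the Investigator". SAP 4.4.1.5 says "Causality is not assessed for solicited AEs".

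On Day 1, medical history, current medical condition, vital signs and a physical examination are collected (Protocol 5.7 and 5.7.1). SAP 6.1.5 codes past and current conditions in MedDRA and tabulates them by SOC and PT.

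**The concern.** The trial has one arm and enrols people aged 65 and over. Several solicited systemic terms (joint pain, muscle pain, fatigue, headache) are also everyday complaints. The exclusion criteria in Protocol 5.2.2 name no chronic joint or muscle complaint, so people who have one can enrol unless the investigator sees an added risk. Take a participant with daily mild joint pain at entry who reports mild joint pain on the card throughout the week. Under Protocol 5.5 this is not an AE. Under SAP 6.2.1 it is one solicited occurrence, and under Protocol 5.5.2 it is vaccine-related.

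No control arm shows how much of the reported rate is background. The *any* rows are exposed. So are the duration statistics and the rows for events still ongoing at the end of Day 7, since an unchanged chronic symptom tends to fill all seven days. The limitations in Protocol 6.4.6 cover inaccurate grading and under-reporting, but not background symptoms.

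**Working it through.** **1. The plan's own precision figure.** For a 10% event rate and N=250, Protocol Table 7 gives an exact interval of 6.58% to 14.41%. Clopper-Pearson limits for 25/250 reproduce it. This interval covers sampling error only and does not address background symptoms.

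**2. Following the rules for one participant.** Assume joint pain present before the dose and unchanged, reported as mild on each of Days 1 to 7.

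- Protocol 5.5: not an AE; recorded as medical history.
- Protocol 5.5.1: entered as a solicited event because the card reports it.
- SAP 6.2.1: occurrence = 1.
- SAP 6.2.2: duration = 7 days.
- SAP 4.4.1.7: can count as ongoing at the end of the solicited period.
- Protocol 5.5.2: deemed vaccine-related.

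Neither document describes a step that applies the first line to the others.

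**3. Size under stated assumptions.** The documents give no background prevalence. Let v be the vaccine-attributable rate of one symptom and b its 7-day background prevalence. Assume that the two are independent and that every affected participant answers yes. Then

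reported rate = v + (1 − v) × b.

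With v = 10%, and counts rounded to whole participants at N=250:

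| b (assumed) | Reported rate | Count | Exact 95% CI |
|---|---|---|---|
| 2% | 0.10 + 0.90 × 0.02 = 11.8% | 30 | 8.2–16.7% |
| 5% | 0.10 + 0.90 × 0.05 = 14.5% | 36 | 10.3–19.4% |
| 10% | 0.10 + 0.90 × 0.10 = 19.0% | 48 | 14.5–24.6% |
| 20% | 0.10 + 0.90 × 0.20 = 28.0% | 70 | 22.5–34.0% |

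The shift is (1 − v) × b, or 1.8 to 18 percentage points. If only a fraction r of affected participants answer yes, b is replaced by r × b and the shift shrinks in proportion.

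**4. Does the interval miss the true 10%?** At b = 2% it does not. At b = 10% and 20% it does. At b = 5% the answer depends on the count and the denominator. SAP 4.2.2 analyses solicited events on the Solicited Safety Set (diary returners), which may be smaller than 250. The planned evaluable number is 250 × (1 − 0.20) = 200.

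- 36/250: 10.3–19.4%, excludes 10%.
- 35/250: 9.9–18.9%, includes 10%.
- 29/200: 9.9–20.2%, includes 10%.

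**5. Causality statements side by side, for solicited systemic events.**

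- Protocol synopsis: left to the investigator, since only local events are automatically related.
- Protocol 5.5.2: all related.
- SAP 4.4.1.5: not assessed.
- Protocol 6.4.2, Protocol 6.4.4 and SAP 4.4.1.7: a *related* row is planned for solicited general events.

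If every event is related by rule, that row duplicates *any*. If causality is not assessed, the row cannot be filled. It carries separate information only under the synopsis rule.

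**The case against.** The strongest reply is that the endpoint is descriptive. No hypothesis is tested (Protocol 6.1), and the proportion reporting a symptom within seven days of vaccination is correctly estimated for what it is. That stands, and it is why the *any* rows should stay. They mislead only when read as vaccine-attributable, a reading that Protocol 5.5.2 invites.

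A reader might infer that no pre-dose record of symptoms exists. The documents do not support this. Protocol 5.5 sends pre-existing symptoms to medical history, Day 1 conditions are coded under SAP 6.1.5, temperature is taken before the dose (Protocol 5.4.4), and vaccination is postponed for fever (Protocol 5.2.2). What is missing is a grade for each of the other solicited symptoms and a link from the Day 1 record to the diary.

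A reader might also infer that the causality sentence itself raises the primary rates. It does not: SAP 4.2.2 counts solicited events regardless of causality and has no *related* row for them. Deleting the sentence would leave the *any* count unchanged. It affects interpretation and the *related* rows elsewhere.

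Finally, the diary instructions and the content of the Day 1 questionnaire survey (Protocol Table 2) are not described in the documents. The card may ask for new or worsened symptoms only, and the under-reporting expected in Protocol 6.4.6 pushes the rates down. Both points limit what can be said about size. Neither supplies a counting rule.

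**Conclusion.** The point holds as a gap between the AE definition and the derivation. Protocol 5.5 excludes unchanged pre-existing symptoms, but nothing in the described diary process or the SAP applies that exclusion to solicited events. Following the plan as written can count such symptoms in the *any*, duration and ongoing results.

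The size cannot be computed from the documents. The range of 11.8% to 28% for a true 10% rests on three assumptions: a 2% to 20% background, independence, and a yes from every affected participant. It would be tempting to say that a 5% background already puts the true rate outside the reported interval. That conclusion is fragile, because it holds at 36/250 but not at 35/250 or 29/200.

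The conflict over causality for solicited systemic events is demonstrable without any assumption. The data remain usable. The change is worth making because the plan as it stands cannot separate background from new symptoms.

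**What to change.** 1. **Before the dose.** Add a short checklist at the existing Day 1 visit recording presence and grade of each solicited symptom on the Protocol Table 3 scale.
2. **Tables.** In SAP 4.2.2 and 4.4.1.7 keep the *any* rows and add a row for solicited events that are new or higher in grade than before the dose. Do the same for duration and ongoing events.
3. **If enrolment has started.** Split the solicited rates by whether a matching preferred term appears in the Day 1 medical history and current conditions data (SAP 6.1.5).
4. **Causality.** Reconcile the synopsis, Protocol 5.5.2 and SAP 4.4.1.5 into one statement for solicited systemic events. Align the *related* rows in Protocol 6.4.2, Protocol 6.4.4 and SAP 4.4.1.7 with it, removing any that cannot be filled.
5. **Limitations.** State in Protocol 6.4.6 that, without a comparison group, the *any* rates include background symptoms.

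The cost is a brief checklist and one extra row per solicited table, with no extra visit or test and no change to the sample size. The medical-history fallback is weaker: it matches imperfectly and carries no pre-dose grade on the Table 3 scale.
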